3.2.1.1 Intra-subject Dose Escalation

During dose escalation, individual patients may be considered for treatment at a dose level of Tenalisib/Romidepsin higher than the dose to which they are initially assigned at investigator's discretion after discussion with Medical Monitor. For a patient to be treated at a higher dose level of Tenalisib/Romidepsin, the patient must not have experienced a DLT at the assigned dose and tolerated the lower dose for at least one cycle of therapy. The patient must have undergone a disease evaluation and been found appropriate to continue on study. (e.g. A patient on Tenalisib 400 mg can be escalated to 600 mg dose once the safety of 600 mg dose is established. For a patient to be treated at 600 mg dose level, the patient must not have experienced a DLT at 400 mg dose and tolerated the dose for at least one cycle of therapy. Similar is the case for Romidepsin)

The new higher dose must be a dose that has completed evaluation and has not exceeded the MTD. The dose escalation can occur at the start of a new cycle. At the discretion of investigator, dose escalation may be done in patient who received lower doses (de-escalation) due to safety reasons.

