3.6 Study Stopping Rules

3.6.1 Stopping Rule for Dose Escalation

The SRC will be in charge of reviewing safety data following the final treatment dose (Day 28 of Cycle 1) of the last patient in each cohort and will decide whether or not it is possible to proceed to the next cohort according to the dose escalation procedure described in Section 3.2.1.1. In order to ensure safety and limit toxicity for enrolled patients, dose modifications will be performed according to the procedure described in Section 7.7.

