7.7 Dose Modifications

All dose modifications are graded by the CTCAE v5.0.

Note: If cytopenia events are deemed related to the underlying disease rather than either Tenalisib or Romidepsin, dose reduction will be done as per the investigator's discretion.

Patients who experience either a DLT or an adverse event meeting DLT criteria (that occurs after the DLT assessment window) will be allowed to delay dosing in order to recover from the toxicity. Patients may resume Tenalisib, provided that the toxicity has resolved to Grade ≤ 2 or baseline. If study drug is delayed >2 weeks due to drug toxicity, treatment initiation should be discussed and agreed with the Medical Monitor.

Dose reductions will be permanent. A dose re-escalation are not permitted for patients who previously had a dose reduction. Holidays from study drug are discouraged. Any patient in whom similar toxicity recurs at the reduced dose should be discontinued from further Tenalisib treatment. Note: In exceptional case, a patient may be allowed following a careful assessment of benefit and risk by the investigator and with approval from the Medical Monitor.

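### In Phase I, the intra-subject escalation section lets a dose lowered for safety be raised again, while Section 7.7 makes reductions permanent and forbids re-escalation; nothing says which rule prevails

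*Protocol*

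**What the plan says.** The section headed Intra-subject Dose Escalation (one of two numbered 3.2.1.1 in the Protocol) allows a Phase I patient to be treated at a dose "higher than the dose to which they are initially assigned at investigator's discretion after discussion with Medical Monitor". Its conditions include that "the patient must not have experienced a DLT at the assigned dose and tolerated the lower dose for at least one cycle of therapy". Also required are a disease evaluation and a judgment that the patient is suitable to continue. The target dose must have been fully evaluated and not exceed the MTD, and the change is made at the start of a cycle. The closing sentence adds that, at the investigator's discretion, "dose escalation may be done in patient who received lower doses (de-escalation) due to safety reasons".

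Section 7.7 (Dose Modifications) states: "Dose reductions will be permanent". It continues: "A dose re-escalation are not permitted for patients who previously had a dose reduction". It then says that a patient whose toxicity recurs at the reduced dose should stop Tenalisib. A note follows, allowing an exceptional case "following a careful assessment of benefit and risk by the investigator and with approval from the Medical Monitor".

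Section 3.6.1 (Stopping Rule for Dose Escalation) ties the two together: "dose modifications will be performed according to the procedure described in Section 7.7".

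SAP 5.1 repeats the general permission for intra-subject escalation and does not address the conflict.

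**The concern.** A site or Medical Monitor who relies on the intra-subject section could return a patient to a dose already lowered for toxicity. One who relies on Section 7.7 could not. This is a safety instruction in a study with about 15 centers, and it should have one answer.

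The control also differs between the two texts. The intra-subject section asks for investigator discretion and discussion with the Medical Monitor. The only exception in Section 7.7 needs the Medical Monitor's approval. In addition, the intra-subject section does not require the toxicity that caused the reduction to have fully resolved before the dose goes back up.

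**Working it through.** The plan states no figure on this point. The check is a comparison of texts, followed by a short count of who and when.

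**1. Same patient, two answers.** Take an escalation-phase patient whose Tenalisib was cut by one level for toxicity that was not a DLT, and who then tolerated the lower dose for a cycle.

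| Source | May the dose be raised again? |
|---|---|
| Protocol, Intra-subject Dose Escalation, last sentence | Yes, at the investigator's discretion |
| Protocol 7.7 | No; the reduction is permanent |
| Protocol 3.6.1 | Sends dose escalation to 7.7 |
| SAP 5.1 | Silent on prior reductions |

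Section 7.7 also covers Phase I in its own words, since it deals with patients who have had a DLT. For Romidepsin, 7.7.3.1 and 7.7.3.2 call the listed reductions permanent. No text gives one rule priority.

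**2. Who passes the no-DLT condition.** Two groups remain.
- Patients reduced for toxicity after the DLT window. The window is 28 days unless the Medical Monitor extends it (7.6.3).
- Patients reduced in Cycle 1 for toxicity that is not a DLT. For example, a Grade 3 ALT/AST elevation that falls to Grade 2 or less within 14 days is exempt under 7.6.2, yet Table 8 restarts Tenalisib one dose lower once it reaches Grade 1 or less. Recovery to Grade 1 must take under 14 days, because a treatment delay of 14 days or more is itself a DLT. The SRC may also class other worrying events as DLTs (7.6.2), which could remove some of this group.

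The example is realistic: AST/ALT elevation is the most frequent treatment-related Grade 3 or higher event listed for the earlier single-agent T-cell lymphoma study (n=12; Protocol 1.1.2). No rate is inferred from it.

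**3. When a post-window reduction could be reversed.**
- Treatment runs from C1D1 to C7D28 (6.1): 7 cycles. The DLT window is Cycle 1, so 7 − 1 = 6 cycles follow it.
- Escalation occurs only at a cycle start. The last start on treatment is C7D1, so a reduction in Cycle 7 cannot be reversed on study.
- One cycle at the lower dose must come first, so reduced dosing must begin by C6D1.
- Reduced dosing that begins in Cycles 2, 3, 4 or 5 qualifies: 4 of 7 cycles, 4/7 = 57%.
- Counting Cycle 6, where only a reduction at its start qualifies, gives at most 5/7 = 71%.

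These are shares of planned treatment time, not probabilities of reduction.

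**4. Population ceiling.** Escalation: 3 cohorts × 6 = 18 at most, unless dose levels are added. Expansion: 2 × 12 = 24. Total 42; 18/42 = 43%. The 18 is the whole escalation part, not the number affected.

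**5. What is already controlled.** The reduced dose starts only after recovery. For Tenalisib the general rule is Grade 2 or less or baseline (7.7), and Table 8 requires Grade 1 or less after Grade 3 ALT/AST elevation. For the Romidepsin reductions it is Grade 1 or less or baseline (7.7.3.1, 7.7.3.2). Under the general Tenalisib rule, residual Grade 2 toxicity can be present when the reduced dose begins, and the intra-subject section does not ask that it clear before re-escalation.

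**The case against.** **Cohort reading.** The cohort escalation text uses *de-escalation* for SRC dose-level decisions, while 7.7 uses *dose reduction* for individuals. The Table 1 footnotes also describe lower-dose cohorts opened because of DLTs. The closing sentence could therefore mean patients enrolled in such a cohort. This is possible but less natural. The sentence sits in an intra-subject section and speaks of a patient who received lower doses. Someone enrolled at a lower level is already covered by the section's opening sentence. Redundancy alone is weak evidence, since the section repeats its own conditions in its worked example, so the fix allows for this reading.

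**Exceptional-case note.** It follows the sentence on recurrence at the reduced dose, so it most naturally concerns continuing Tenalisib. Even if stretched to cover re-escalation, it requires an exceptional case and Medical Monitor approval, which the intra-subject section does not.

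**Romidepsin discretion.** Section 7.7.3 leaves the investigator final discretion over how aggressive and how many reductions are, and the permanent reductions apply only to listed events. That limits the weight of the Romidepsin rules, but discretion over reducing does not authorise re-escalation.

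**Medical Monitor as common check.** The sponsor supplies the monitor (12.3), and discussion is required, so sites would not settle the matter alone. This lowers the risk of divergence. The monitor would still be working from two opposite texts.

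**Recovery and SRC powers.** Both stand, as set out in the working, and both narrow the point.

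**Conclusion.** The conflict is real on the patient-level reading and should be fixed. It covers at most 18 escalation-phase patients, unless dose levels are added, and among them only those reduced for non-DLT or post-window toxicity. For post-window reductions, about 4 to 5 of the 7 cycles are relevant. The documents give no basis for estimating how many patients would be reduced and then re-escalated.

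This assumes that the section's general conditions, including one cycle tolerated at the reduced dose, also govern its last sentence.

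A reader might infer more in three respects, and the documents do not support it:
- *All 6 of 7 post-window cycles (86%) are exposed.* This ignores the cycle-start and one-cycle conditions and the end of treatment at C7D28.
- *Patients could be re-escalated with no recovery required at all.* Recovery is required before the reduced dose starts; what is missing is full resolution before the increase.
- *The MTD or the Phase II results are compromised.* The MTD rule counts DLTs in Cycle 1 (7.6.4), re-escalation comes only after at least one cycle, and the permission applies during dose escalation only.

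**What to change.** Replace the closing sentence of Intra-subject Dose Escalation with: *Patients whose dose was reduced for toxicity are not eligible for intra-subject escalation; see Section 7.7.*

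If the sponsor intends an exception, state it once in Section 7.7, require that the toxicity has resolved and that the Medical Monitor approves, keep the existing conditions, and cross-refer from 3.2.1.1. In that case a SAP listing of re-escalated patients, with adverse events by dose at onset, would be a useful addition.

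If cohort-level de-escalation was meant, say so in the sentence.

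The cost is one Protocol sentence and a cross-reference or, with an exception, a short paragraph and one listing. Sample size, the MTD rule and the efficacy analysis do not change.

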3.2.1.2 Alternative Dosing Cohorts

Depending on nature and timing of the toxicities, pharmacokinetic data of Tenalisib/Romidepsin, alternative dosing regimens and schedules may be examined. If in the opinion of the SRC, observed toxicities (DLTs and/or non-dose limiting adverse events of concern) are likely to have resulted from a continuous exposure to the study drug or cumulative effect, alternative dosing regimens or schedules may be explored. The SRC will determine an alternative schedule, based on PK data, nature and timing of toxicities, and the

recovery periods of the observed toxicities. Dose escalation will be continued with an alternative schedule till determination of the MTD/optimal dose of the combination.

3.2.2 Phase II: Dose Expansion

After establishing the MTD/optimal dose, the Phase II (Dose Expansion) will be opened as approved by the SRC to enroll two groups of patients.

Table 2: Dose Expansion

Group	N	Patient population	Tenalisib	Romidepsin
Group 1	12	R/R PTCL	MTD/Optimal dose	MTD/Optimal dose on Day 1, 8 and 15
Group 2	12	R/R CTCL	MTD/Optimal dose	MTD/Optimal dose on Day 1, 8 and 15

3.3 Randomization and Blinding

This is a non-randomized, open label study.

3.4 Investigational Medicinal Product

3.4.1 Dosage Form and Strengths

Investigational Product(s)	Dosage form, strength	Manufacturer
Tenalisib	Tablets; 200 mg and 400 mg.	STA Pharma Co., Ltd
Romidepsin	10 mg single-dose vial	For Romidepsin, please refer to prescribing information.

Note: Please refer *Investigator's Brochure* for additional information of Tenalisib. For Romidepsin, please refer to prescribing information.

3.4.2 Labeling, Packaging and Supply

• Tenalisib

Tenalisib will be supplied through Rhizen Pharmaceuticals SA. Tenalisib will be available in 30 tablets per High-density Polyethylene (HDPE) bottle. All trial drugs must be kept in a secure place at below 25°C (77°F), protected from moisture”.

• Romidepsin

Commercially available Romidepsin will be used. Please refer to **Appendix H** for storage conditions and handling of Romidepsin.

3.4.3 Preparation and Administration of Investigational Products

3.4.3.1 Tenalisib

At the start of each cycle, sufficient quantity of Tenalisib will be dispensed. Study drug compliance should be reviewed with the patient at the beginning of each new treatment cycle. Study drug compliance must be documented, including missed doses and subject re-education and dose administration.

Guideline for Administration of Tenalisib:

- Method of Administration: Tenalisib will be administered orally twice daily in a 28-day cycle (Day 1-28). Only during Cycle 1 of Dose Escalation, Tenalisib will be given starting from Day 3 (i.e. C1D3) to permit PK assessment of Romidepsin alone. Patients will be, therefore, instructed to start Tenalisib treatment on C1D3 and will be informed that they will receive Tenalisib for only 25 days in the first cycle.
- Pre-medications: None for Tenalisib. However, routine prophylactic anti-emetics or pre-medications may be required for Romidepsin.
- Tenalisib tablets will be self-administered orally twice daily one hour before a major meal (e.g. breakfast and dinner). Patients should not consume food during this one-hour period.
- Tenalisib tablets should be taken at approximately same time each day. Tablets should be swallowed; and should NOT be crushed or chewed.
- If a dose of Tenalisib is missed, it should be taken as soon as possible on same day with an interval of 8 hours between two doses. If it is missed for the entire day, it should not be repeated. If vomiting occurs, no attempt should be made to replace the vomited dose.
- Study drug compliance should be reviewed with the patient at the beginning of each new treatment cycle. Missed doses should be documented.
- On the day of Romidepsin administration, the morning dose of Tenalisib should be given in clinic one hour prior to Romidepsin infusion.

3.4.3.2 Romidepsin

Romidepsin will be supplied as a standard kit. Below is the general outline of preparation and administration of Romidepsin. However, please refer the Prescribing information for these instructions.

• Preparation of Romidepsin

- Romidepsin must be reconstituted with the supplied diluent and further diluted with 0.9% Sodium Chloride Injection, USP before intravenous infusion.
- Romidepsin and diluent vials contain an overfill to ensure the recommended volume can be withdrawn at a concentration of 5 mg/mL

• Preparation for Intravenous Administration

- Each 10 mg single-dose vial of Romidepsin must be reconstituted with 2.2 mL of the supplied diluent.
- With a suitable syringe, aseptically withdraw 2.2 mL from the supplied diluent vial, and slowly inject it into the Romidepsin for injection vial. Swirl the contents of the vial until there are no visible particles in the resulting solution.
- The reconstituted solution will contain Romidepsin 5 mg/mL. The reconstituted Romidepsin vial will contain 2 mL of deliverable volume of drug product. The

reconstituted Romidepsin solution is chemically stable for up to 8 hours at room temperature.

- Extract the appropriate amount of Romidepsin from the vials to deliver the desired dose, using proper aseptic technique. Before intravenous infusion, further dilute Romidepsin in 500 mL 0.9% Sodium Chloride Injection, USP.
- Infuse over 4 hours.

Guideline for Administration of Romidepsin:

- Method of administration: Romidepsin will be administered as an intravenous infusion in outpatient basis/ hospital setting.
- **Pre-medications:**
 - Nausea and vomiting are common following treatment with Romidepsin, therefore **prophylactic antiemetics** are recommended for all patients. Advise patients to report these symptoms so that appropriate treatment can be instituted the earliest. Due to potential for CYP3A4 interaction, administration of a neurokinin-1 receptor inhibitor antiemetics (e.g. aprepitant, fosaprepitant) is not permitted.
 - Patients with advanced stage disease and/or high tumor burden are at the risk of tumor lysis syndrome, therefore these patients are advised to maintain **high fluid intake** for at least 72 hours after each dose.
- Serum potassium and magnesium should be \leq ULN before Romidepsin treatment.
- Trial treatment should be administered on Day 1, Day 8 and Day 15 of each cycle of 28 days. Interruptions from the treatment plan may be allowed for toxicity management, but require consultation between the investigator and Sponsor, and written documentation of the collaborative decision on subject management.
- All trial treatments will be administered on an outpatient basis.
- **Romidepsin should be infused over 4 hours.** Sites should make every effort to target infusion timing to be as close to 4 hours as possible. However, given the variability of infusion pumps from site to site, a window of -5 minutes and +10 minutes is permitted.
- Romidepsin must be stored as per prescribing information. .
- Prescribing information should be referred for specific instructions for Romidepsin reconstitution, preparation of the infusion fluid, and administration.

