3.4.5.2 Romidepsin

The following adverse events have been reported in patients receiving Romidepsin:

- Myelosuppression: Romidepsin can cause thrombocytopenia, leukopenia (neutropenia and lymphopenia), and anemia; monitor blood counts during treatment with Romidepsin; interrupt and/or modify the dose as necessary.
- Fatal and serious infections, including pneumonia, sepsis, and viral reactivation, including Epstein Barr and Hepatitis B viruses, have been reported in clinical trials with Romidepsin. These can occur during treatment and within 30 days after treatment. The risk of life-threatening infections may be greater in patients with a history of prior treatment with monoclonal antibodies directed against lymphocyte antigens and in patients with disease involvement of the bone marrow.
- Several treatment-emergent morphological changes in ECGs (including T-wave and ST-segment changes) have been reported in clinical studies. The clinical significance of these changes is unknown.
- Tumor lysis syndrome (TLS) has been reported to occur in 1% of patients with tumor stage CTCL and 2% of patients with Stage III/IV PTCL. Patients with advanced stage disease and/or high tumor burden are at greater risk, should be closely monitored, and managed as appropriate.
- Since Romidepsin is a substrate of CYP3A4 enzymes, concomitant administration of CYP3A4 inhibitor or inducer may interact with Romidepsin. If concomitant treatment of these drugs is clinically warranted, careful observation of the patient is advised.

Strong inhibitor or inducers should be avoided as directed in Section on prohibited medication.

Please refer to the full prescribing information of Romidepsin for additional safety information.

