14. Subjects with concomitant second malignancies (except adequately treated non-melanomatous skin cancers, ductal carcinoma in situ, superficial bladder cancer, prostate cancer or in situ cervical cancers) are excluded unless a complete remission is achieved at least 2 years prior to study entry and no additional therapy (except adjuvant or maintenance therapy to reduce the risk of recurrence) is required or anticipated to be required during the study period.
15. Administration of any of the following within 1 week prior to C1D1:
 - Strong inhibitors or inducers of CYP3A4 including but not limited to grapefruit products, herbal supplements and drugs
 - Strong inhibitors or inducers of CYP2C9 including but not limited to herbal supplements and drugs
 - Substrates of CYP3A4 enzyme with a narrow therapeutic range.
16. History of Grade 4 anaphylactic reaction.
17. Administration of live vaccines within 6 weeks of C1D1.
18. History of prior surgery or gastrointestinal dysfunction that may affect drug absorption (e.g., gastric bypass surgery, gastrectomy)
19. Current history of a serious uncontrolled medical disorder, metabolic dysfunction, physical examination findings, or clinical laboratory findings giving reasonable suspicion of a disease or condition that contraindicates use of an investigational drugs or render the subject at high risk from treatment complications.
20. Uncontrolled or significant cardiovascular disease including, but not limited to:

- Congenital long QT syndrome.
- QTcF interval > 450 msec
- Myocardial infarction or stroke/TIA within the past 6 months
- Uncontrolled angina within the past 3 months
- Significant ECG abnormalities including 2nd degree atrio- ventricular (AV) block (AV) block type II, 3rd degree AV block
- History of clinically significant arrhythmias (such as ventricular tachycardia, ventricular fibrillation or torsades de pointes)
- History of other clinically significant heart disease (ie, cardiomyopathy, congestive heart failure with NYHA functional classification III-IV, pericarditis, significant pericardial effusion)
- Requirement for daily supplemental oxygen therapy.

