6.4 Laboratory Investigations

Laboratory tests for hematology, chemistry and urinalysis are specified in Table 4.

Table 4: Laboratory Tests for Hematology, Chemistry and Urinalysis

Hematology	Chemistry Panel I	Chemistry Panel II	Urinalysis	Other
Hematocrit	Total bilirubin	Blood glucose	Blood	Serum β -hCG
Hemoglobin	Alkaline phosphatase (ALP)	Urea or blood urea nitrogen ^a	Glucose	Urine pregnancy test
CBC with differentials	Alanine aminotransferase (ALT)	Creatinine	Protein	PT/INR
Platelet count	Aspartate aminotransferase (AST)	Albumin	Specific gravity	Serology (Only at Screening) (Hepatitis B, Hepatitis C, HIV, EBV and CMV)
WBC (Total and differentials)	Lactate dehydrogenase (LDH)	Total protein	Microscopic exam ^b	
Red blood cell count	Gamma-glutamyl transferase (GGT)	Total Cholesterol		
Absolute neutrophil count	Sodium	Triglyceride (TG)		
Absolute lymphocyte count	Potassium	LDL		
	Calcium	HDL		
	Phosphorous	TSH		
	Bicarbonate or Carbon dioxide (CO2)	T3 (Total or Free)		
	Chloride	T4 (free)		
	Magnesium			

^a Blood Urea Nitrogen is preferred; if not available Urea may be tested.

^b Microscopic exam, if abnormal results are noted

Blood drawn for these tests will be specified in informed consent form (ICF). The investigations will be performed at each local laboratory. Additional details will be provided in the study-specific Laboratory Manual.

Screening labs will be done within 7 calendar days prior to the initiation of trial treatment. If these initial examinations are obtained within 72 hours of Cycle 1 Day 1, the labs need not be repeated. Re-screening can be done at the discretion of PI. Scans and other investigations

to document measurable disease should be performed ≤ 28 weeks prior to initiation of treatment.

6.5 12-Lead Electrocardiograms

An ECG will be performed at the time points mentioned below table. Additional ECGs will be obtained if clinically indicated. A single ECG will be performed at all-time points unless specified. Triplicate ECGs only need to be performed at other time points to confirm the significant changes of single ECG (e.g. If QTcF > 450 msec on single EKG at screening or > 500 msec during treatment). All ECGs will be performed on local equipment. Window period of ± 5 minutes will be applicable to 30 min time point. For all time 1 hr time points, ± 15 minutes window period will be applicable.

Dose Escalation		
Days	Time points	Note
Screening	Within last 28 days	-

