C1D1	All PK matched time points (Pre-infusion (0), 1, 2, 3, 5, 7, 9, 10 hrs).	Time points are with respect to Romidepsin infusion.
C1D8	All PK matched time points (Pre-dose (0), 0.5, 1 (pre-infusion of Romidepsin), 2, 3, 4, 6, 8, 10, 11 hrs post-dose).	Time points are with respect to Tenalisib dosing
C1D15	Before-infusion and immediately after infusion.	Time points are with respect to Romidepsin infusion.
Rest of the cycles (Day 1 of each cycle)	Before-infusion and immediately after infusion.	Time points are with respect to Romidepsin infusion.

Dose Expansion		
Days	Time points	Note
Screening	Within last 28 days	-
Day 1 of each cycle	Before Romidepsin infusion.	

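### The protocol body's only potassium and magnesium limit before Romidepsin is an upper one, so any low value meets it

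*Protocol*

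**What the plan says.** The administration guideline in Protocol 3.4.3.2 states: "Serum potassium and magnesium should be" ≤ "ULN before Romidepsin treatment". The section presents itself as an outline and points to the label: "However, please refer the Prescribing information for these instructions". The label is Appendix H, and its text is not among the documents available here.

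Other relevant statements in the protocol:

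- **3.4.5.2**, on Romidepsin risks: "Several treatment-emergent morphological changes in ECGs (including T-wave and ST-segment changes) have been reported in clinical studies". Their clinical significance is described as unknown, and QT is not mentioned.
- **4.2, exclusion 19** covers "metabolic dysfunction, physical examination findings, or clinical laboratory findings giving reasonable suspicion of a disease or condition" that would contraindicate treatment or put the patient at high risk. It gives no electrolyte figure.
- **6.4**, on screening laboratory tests: "If these initial examinations are obtained within 72 hours of Cycle 1 Day 1, the labs need not be repeated".
- **3.4.3.2**, on departures from the dosing schedule: "Interruptions from the treatment plan may be allowed for toxicity management, but require consultation between the investigator and Sponsor".
- **Table 8, Cardiac row**: after QTcF above 500 msec the dose is held and potassium and magnesium are to be attended to at once. The row gives no target value and sits in the Tenalisib modification section.

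**The concern.** A limit meant to make an infusion safe would be expected to exclude the values thought to be unsafe. The protocol links these two analytes to QT prolongation in Table 8, but only after the event. Its one preventive threshold screens out high values and lets every low value through.

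A site that follows the sentence literally can infuse at a low potassium or magnesium, and the body does not say what to do with such a result before dosing. What is at stake is patient safety on infusion days. No planned estimate or test depends on the sentence.

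**Working it through.** The protocol gives no figure to reproduce and no formula applies. The check is logical, followed by a comparison of the sections that could supply a lower limit.

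**1. Direction of the limit.** LLN lies below ULN. If a value x is below LLN, then x is below ULN, so x satisfies ≤ ULN. This holds for a low value of any grade.

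**2. Search for a lower limit elsewhere.**

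| Place | What it sets | Lower limit for K or Mg? |
|---|---|---|
| 4.1, inclusion 9 | Hemoglobin, ANC, platelets, bilirubin, AST/ALT, creatinine clearance | No |
| 4.2, exclusion 19 | Investigator's judgement on metabolic or laboratory findings, at entry | No |
| 4.2, exclusion 20 | Long QT syndrome, QTcF above 450 msec, arrhythmia, other heart disease, at entry | No |
| 6.4 and Table 4 | Both analytes listed in Chemistry Panel I | No |
| Table 8 (Tenalisib) | Action after QTcF above 500 msec | No |
| 7.7.3 to 7.7.3.2 (Romidepsin) | Delay by toxicity grade; no electrolyte or QTc rule | No |
| SAP 10.6.3 | Descriptive summaries and a listing of abnormal values | No |

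**3. What the other rules catch.**

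- *New low values of Grade 2 or higher.* Section 7.7.3.2 delays Romidepsin until Grade 1 or less, or baseline. Section 7.7.3 makes this depend on the investigator attributing the toxicity to Romidepsin. Sections 7.2 and 7.6 treat toxicities as related unless another cause is clear, so most such values should be caught.
- *Grade 1 low values.* These do not trigger 7.7.3.2, and they also satisfy its restart condition.
- *Low values present at entry and unchanged.* These satisfy the baseline alternative in the restart condition. Exclusion 19 could have kept the patient out, but only by judgement and only at entry.
- *Higher-grade low values clearly due to another cause.* These also pass, but the default to related makes this a smaller remainder.
- *Recording.* Under 7.4.3 a Grade 1 or 2 laboratory value becomes an adverse event only if it is clinically significant, so many mild low values would not enter adverse-event review.

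The uncovered remainder is therefore mainly Grade 1 and stable baseline-level low values.

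**4. Whether the data needed for a rule exist.** Tables 5 and 6 schedule Chemistry Panel I on Days 1, 8 and 15 of Cycles 1 to 7. Infusions per patient are 3 × 7 = 21, and all 21 infusion days have a scheduled draw (C1D1 may use results from within 72 hours). The measurements are already planned. What is missing is an instruction for a low result.

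**The case against.** **The label governs.** Section 3.4.3.2 defers to the prescribing information, and 3.4.5.2 sends the reader there for further safety information. If Appendix H sets a lower limit, the trial already has one and the body sentence is merely an incomplete summary. This stands as a limit on the claim, which covers the protocol body only. It does not make the sentence sound: a site using the body alone would still read a one-sided limit.

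**The upper limit may be deliberate.** The sentence follows the advice on tumor lysis, where high potassium is a plausible worry. That does not explain magnesium, and keeping ≤ ULN while adding ≥ LLN preserves any such purpose.

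**The harm is not shown.** Section 3.4.5.2 does not mention QT for Romidepsin, and the documents give no rate of low values. Both points stand. The link from low values to QT risk is a clinical assumption, with Table 8 as the only support in the text.

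**Safeguards exist.** Exclusion 20 removes the patients at highest QT risk. The default to related strengthens the Grade 2 delay. Where both drugs may be responsible, 7.7.2 takes the more cautious course. Significant ECG changes are confirmed in triplicate (6.5), and the medical monitor reviews all adverse events (12.3). These provisions narrow the gap to mild and baseline-level values. None sets a lower limit.

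**Requiring ≥ LLN causes conflicts of its own.** It contradicts restart at Grade 1 or baseline in 7.7.3.2. A delay after the clinic Tenalisib dose would also break the one-hour interval before infusion and the C1D8 PK and ECG times, which run from that dose (6.5, 6.10), and 3.2.1.1 makes C1D8 PK data essential for escalation decisions. These objections are correct, and the fix has to deal with them.

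**Conclusion.** The point holds in limited form. In the protocol body the only pre-Romidepsin threshold for potassium and magnesium is an upper one, and every low value meets it. Once the other rules are counted, mainly Grade 1 and stable baseline-level low values remain uncovered. Severity is minor to should-fix. The frequency of such values and any excess risk cannot be derived from the documents.

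The conclusion rests on two assumptions: that low values are clinically relevant to QT, and that Appendix H does not already settle the matter for sites.

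A reader might infer more in three ways, none of which the documents support:

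- *That severe low values go unchecked.* The Grade 2 delay and the default to related cover most of them.
- *That the protocol contradicts the label, or that the sign is a misprint.* The label text is not available, and nothing in the documents shows what was intended.
- *That ECG coverage measures the problem.* In the expansion part, ECGs are scheduled on 7 of the 21 infusion days, leaving 21 − 7 = 14 without one. That counts infusions without a scheduled ECG, not infusions given at a low value. It would also be unchanged by correcting the sentence, so it carries no weight here.

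**What to change.** Amend the protocol as follows:

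1. **3.4.3.2.** Replace the sentence with: *Before each Romidepsin infusion, potassium and magnesium should both lie within the normal range (≥ LLN and ≤ ULN); a low value should be corrected before dosing.* The clinical team should confirm this limit against Appendix H.
2. **Timing.** State that the Chemistry Panel I results scheduled for Days 1, 8 and 15 are the ones used, with the 72-hour allowance kept for C1D1. They are to be reviewed before the morning clinic dose of Tenalisib, so that the one-hour interval and the C1D8 PK and ECG times are kept. On C1D1 of dose escalation, when Tenalisib has not yet started, review comes before the infusion.
3. **7.7.3.2.** Add that this requirement takes precedence over restart at Grade 1 or less, or baseline.
4. **Delays.** State that a short correction delay within the existing visit window needs no Sponsor consultation under 3.4.3.2, and that longer delays keep that step.

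The cost is a short amendment to two sections, a notice to sites, an occasional repeat electrolyte test and an occasional short infusion delay. No new scheduled test is needed.
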